11.1.5 Motivations, Attitudes, and Expectations Form

Motivation for participating in the study and attitudes and expectations regarding study medication are collected once at screening.

11.1.6 Treatment Satisfaction Survey

Satisfaction with treatment is recorded on the Treatment Satisfaction Survey completed at the end-of-treatment visit (EOT/week 24).

11.1.7 Relapse

Relapse criteria is reviewed at each research visit beginning with visit 4 (since relapse by definition cannot occur before Day 21) and continuing through the end-of-treatment visit (EOT/week 24). This form documents the time to event.

11.1.8 Continuing Treatment Forms

At the conclusion of study treatment, participants are discharged to treatment in the community. These forms document the treatment plan identified for the participant at week 24 or at the end of treatment visit if treatment is stopped early. At the 2 follow up visits (weeks 28 and 36/EOS), participants are asked whether they are adhering to the treatment plan, have initiated other treatment or discontinued all treatment.

11.1.9 Study Termination Form

This form tracks the participant's status in the study. It is completed at the week 36/EOS visit or once the week 36 follow-up visit window lapses for participants who do not complete this final follow-up. This form is used in data analyses to address variables such as treatment retention and completion.

11.2 Safety and Medical

The study physician must review and approve all safety and eligibility assessments in order to confirm participant eligibility prior to randomization.

11.2.1 Medical and Psychiatric History

The study clinician obtains a medical and psychiatric history from the participant covering past and present health conditions to help determine eligibility and to provide baseline information. This is collected during screening. This information may be used in data analyses.

11.2.2 Physical Examination

The study clinician completes a physical examination, including blood pressure and heart rate, to ensure that there are no medical concerns regarding participation and to gather baseline information regarding the participant's physical health. During the screening physical exam, a description of the participant's body habitus is documented and the study clinician examines the planned injection sites to ensure adequacy for XR-NTX gluteal intramuscular injection of naltrexone with the supplied needle. The physical examination is performed at screening and is repeated at the end-of-medication visit (if medication is stopped early) or at the end-of-treatment visit (week 24). The physical exam, blood pressure and/or heart rate may be repeated at MM visits at the discretion of the medical clinician.

11.2.3 DSM-5 Criteria

The DSM-5 criteria is applied to determine a current diagnosis for substance use disorder. This is completed at screening to determine eligibility.

11.2.4 Concise Health Risk Tracking-Self Report (CHRT-SR)

The CHRT-SR⁶⁴ is a 16-item participant self-report assessment of suicidality and related thoughts and behaviors. The scale is designed to quickly and easily track suicidality in a manner consistent with the Columbia Classification Algorithm of Suicide Assessment (C-CASA).⁶⁵ The CHRT-SR is assessed at screening, induction, at subsequent MM visits and at the week 28 and

36/EOS visits. The CHRT-SR will assess high risk suicide ideation by a positive response (Agree or Strongly Agree) on any of the last three questions (thoughts of, thoughts of how and/or a specific plan to commit suicide) and prompt a clinician assessment for suicide risk before leaving the clinic.

11.2.5 Clinical Laboratory Tests

Liver function tests (LFTs, consisting of AST, ALT, albumin and bilirubin) and urine pregnancy test (for females) are performed to help determine eligibility at screening. Receipt and review of laboratory test results is necessary before confirming eligibility, conducting randomization and starting study medication. Results of LFTs conducted within four weeks prior to randomization (e.g., collected as part of routine detoxification admission) are acceptable. For participants whose induction onto their assigned study medication is delayed for longer than 2 weeks after randomization, LFTs and urine pregnancy should be repeated prior to start of study medication.

At screening, blood is collected for HIV antibody, hepatitis C virus (HCV) antibody and hepatitis B surface antigen (HBsAG) and hepatitis B surface antibody (HBsAB) tests. These tests do not determine eligibility and are only conducted on samples from participants who are randomized. Results of HIV antibody, hepatitis C virus (HCV) antibody and hepatitis B surface antigen (HBsAG) and hepatitis B surface antibody (HBsAB) tests conducted within four weeks prior to randomization (e.g., collected as part of routine detoxification admission) are acceptable.

For participants whose induction onto their assigned study medication occurs within 2 weeks of Day 0, LFTs are repeated at week 4, week 12, and at the end-of-medication visit (if medication is stopped early) or at the end-of-treatment visit (week 24). For participants whose induction onto their assigned study medication occurs more than 2 weeks after day 0, LFTs are repeated approximately 4 and 12 weeks following induction (a +/- 2 week window for post-induction LFTs is permitted), and at the end-of-medication visit (if medication is stopped early) or at the end-of-treatment visit (week 24). For participants who do not get inducted but continue on study, LFTs need not to be repeated at any of the planned visits with scheduled LFTs.

A laboratory that is accredited by the College of American Pathologists (CAP) or equivalent, and participates in the Clinical Laboratory Improvement Act of 1998 (CLIA) will perform these analyses. The laboratory will provide normal values and proof of lab certifications.

11.2.6 Pregnancy and Birth Control Assessment

This form documents that pregnancy tests were administered, test results, and breast feeding status. The pregnancy and birth control assessment, including on-site urine pregnancy tests, is conducted at screening and may be repeated prior to randomization and/or induction. Birth control assessment and urine pregnancy tests are repeated monthly and at the end-of-medication visit (if medication is stopped early) or at the end-of-treatment visit (week 24).

11.2.7 Adverse Events (AEs) and Serious Adverse Events (SAEs)

At each medical management visit the study clinician assesses for AEs and SAEs by asking the study participant, "How have you been feeling since your last visit?" AEs and SAEs may also be spontaneously reported to study staff at any visit following consent. AEs and SAEs suggesting medical or psychiatric deterioration will be brought to the attention of a study clinician for further evaluation and management. Medical management visits will emphasize overdose risk and risk-management; any reported overdose is recorded as an AE or SAE. AE and SAE reporting is according to the reporting definitions and procedures outlined in the protocol and in accordance with applicable regulatory requirements.

For the purpose of this study, the following AEs do not require reporting in the data system but is captured in the source documentation as medically indicated:

- Grade 1 (mild) unrelated adverse events

This would typically include mild physical events such as headache, cold, etc., that were considered not reasonably associated with the use of the study drug/intervention.

Events related to the injection of the study medication are recorded on the Injection Site Abnormality (INA) form and will not be duplicate-reported on an AE form. Events related to withdrawal symptoms are captured on the SOWS and HAM-D and will not be duplicate-reported on an AE form. Withdrawal symptoms not captured by the SOWS or HAM-D should be reported as an AE. Events captured on study specific forms (INA, SOWS, HAM-D) are not recorded separately as an AE, unless they meet the SAE definition. Any of these events that meet the definition of an SAE are reported on the AE/SAE form set. Any spontaneous reporting of withdrawal symptoms by the participant are captured on AE form in the following situations: withdrawal symptoms reported at visits without scheduled specific structured questionnaires (SOWS, HAM-D); and withdrawal symptoms not listed in the specific structured questionnaires (SOWS, HAM-D) reported at any visit.

11.2.8 Injection Site Examination

Appropriately qualified and trained medical personnel will examine the injection site on the next Medical Management visit following the XR-NTX administration. Participants are asked to immediately report any injection site reactions to study staff for evaluation, monitoring, and possible referral, as needed. Injection site reactions should be documented on the Injection Site Abnormality Log.

11.3 Compliance

11.3.1 Dose Logs

XR-NTX dosing is captured in the MM progress note and recorded in the appropriate CRF and dose log. A BUP-NX dose log documents the amount of medication dispensed for take-home dosing and reported as taken by the participant. These forms are completed at relevant clinic visits through the end of the active treatment phase.

11.3.2 Medical Management

A Medical Management attendance log is completed to document attendance or non-attendance at each Medical Management session during the active treatment phase. The Medical Management discontinuation form is completed when MM visits end (at week 24 post-randomization, when the primary outcome of opioid relapse is met, or for other reasons as determined by the study clinician).

11.3.3 Psychosocial Participation

At each weekly treatment visit, participants are asked to report on their participation in psychosocial TAU during the prior week.

11.4 Drug Use and Psychological

11.4.1 Timeline Follow-Back (TLFB)

The Timeline Follow-Back^{66, 67} procedure is used to elicit the participant's self-reported use of substances before and during the entire study period. At screening, this form is used to assess substance use reported by the participant for the 30-day period prior to admission to detox. During detox, the TLFB is not captured in the data system until the date of discharge. The TLFB is administered at each study visit throughout the active treatment phase and through the end of the follow-up period to document the participant's self-reported use of substances for each day since the previous TLFB assessment.

11.4.2 Urine Drug Screen (UDS)

Urine drug screens are collected at screening, as part of XR-NTX induction, weekly from week 1 through week 24/EOT, and at follow-up visits at weeks 28 and 36/EOS. In most cases the UDS should be completed before assessing self-reported drug use or dispensing medications. All urine specimens are collected using FDA-approved one-step temperature-controlled urine drug test cups following all of the manufacturer's recommended procedures. The UDS tests for the presence of the following drugs: opioids, oxycodone, barbiturates, benzodiazepines, cocaine, amphetamine, methamphetamine, marijuana, methadone, buprenorphine, and ecstasy (MDMA). In the event urine specimen tampering is suspected, either based on the observation or the adulterant tests, study staff should request a second urine sample and may observe the urine collection process according to clinic standard operating procedures. A further validity check is performed using a commercially available adulterant test strip.

11.4.3 Addiction Severity Index Lite (ASI-Lite)

The ASI-Lite is derived from the Fifth Edition of the ASI⁶⁸, a structured clinical interview that yields scores for seven areas of functioning typically impacted by addiction, including medical status, employment status, drug use, alcohol use, family status, legal status, and psychiatric status. Opioid use questions, including the main type of opioid used by the participant, whether a prescription opioid or heroin, the onset of the use, the participant's perception of the substance that is most problematic, and their present treatment goal will also be assessed at screening as part of the ASI assessment. The ASI-Lite is completed at baseline, at the end-of-treatment visit (week 24/EOT), and at the week 36/EOS follow-up visit.

11.4.4 Visual Analog Scales (VAS)

Participants' cravings for opioids, alcohol, and other drugs are documented on visual analog scales (VAS) that range from 0 (no craving) to 100 (most intense craving possible). These scales are completed for opioid craving at screening and at each study visit throughout the active treatment phase, at the end-of-treatment visit (week 24/EOT), and at each follow-up. They are completed for alcohol, stimulants and tobacco craving at screening, weeks 4, 8, 12, 16, 20, 24/EOT, 28, and 36/EOS. VAS also documents responses to opioid use, in the event that participants use opioids during the study.

11.4.5 The Hamilton Depression Scale (17 item) (HAM-D)

The 17-item Hamilton Depression Scale (HAM-D) is a clinician-administered instrument, useful for following both depression and suicidal ideation, and also for following typical symptoms of subacute withdrawal (e.g., low appetite, fatigue, poor sleep). For the purpose of this study, adequately trained research staff conduct the Hamilton Depression Scale (HAM-D).

The HAM-D is completed at screening, at weeks 1, 2, 3, 4, 8, 12, 16 and 20, at the end-of-treatment visit (week 24/EOT), and at each follow-up. A score of 1 or more to item 3 (suicidality) prompts a clinician assessment for suicide risk before leaving the clinic.

11.4.6 The Subjective Opioid Withdrawal Scale (SOWS)

This scale is useful for following self-reported opioid withdrawal symptoms. It is administered at baseline, induction, weekly during the first month after randomization, and at weeks 8, 12, 16, and 20, at the end of treatment (EOT/week 24), and at each follow-up. At the induction visit for the XR-NTX group the SOWS is administered three times, the first time within the hour prior to the naloxone challenge, the second time 10-30 minutes following the naloxone challenge, and the third time 1-3 hours following the XR-NTX injection. At the induction visit for the BUP-NX group, the SOWS is administered twice, the first time within the hour prior to BUP-NX dosing and the second time 1-3 hours following dosing.

11.4.7 Fagerström Test for Nicotine Dependence (FTND)

The Fagerström Test for Nicotine Dependence (FTND) is used for assessing nicotine dependence^{69,70} and is administered at baseline.

11.4.8 Risk Assessment Battery (RAB)

The Risk Assessment Battery (RAB)⁷¹ is a self-administered assessment of engagement in activities that increase the likelihood of contracting HIV. Several scores that measure drug risk, sex risk, and total risk are computed. This measure is completed at baseline, at week 12, and at the end-of-treatment visit (week 24/EOT), and at the week 36/EOS follow-up visit.

11.4.9 Cognitive Function Tests

Cognitive function is assessed using simple, brief, pen and paper tests (Trail Making Test, Parts A and B, and Stroop). These tests are completed at baseline, week 4, 8, 16, and at the end-of-treatment visit (EOT/week 24).

11.4.10 Detoxification Utilization Form

Data on detoxification, including number of days on the unit and medications received, is collected.

11.4.11 EuroQol (EQ-5D)

The EuroQol instrument is a standardized generalized (non disease-specific) system for describing and valuing health-related quality of life. The instrument consists of two components; the EuroQol classification instrument, which describes the respondent's health within 5 domains, and a visual analogue scale with which respondents rate their health. Responses to each component yield a preference weight that can be used to construct Quality-Adjusted Life Year estimates (QALYs). The EuroQol instrument is the recommended Health Quality Index for Economic Evaluations in the Substance Abuse and Addiction Collection of the PhenX Toolkit (www.phenxtoolkit.org). The EQ-5D is completed at baseline, week 4, 8, 12, 16, 20, and 24, at the 2 follow up visits, at the EOT visit if treatment ends early and at the EOS visit if not done at week 36.

11.4.12 Non-Study Medical and Other Services (NMS)

Medical services that are not part of the treatment intervention are recorded on the NMS form. The NMS form captures services received outside the study and CTP including therapy visits,

physician visits, subsequent residential or hospital detoxification, hospital visits and emergency room visits and medication use through participant self-report. The assessment also captures health insurance status, employment, criminal activities, and contact with the criminal justice system. Validity of self-reported health care utilization has been demonstrated.⁷²⁻⁷⁴ The NMS is completed at baseline, week 4, 8, 12, 16, 20, and 24, at the 2 follow up visits, at the EOT visit if treatment ends early and at the EOS visit if not done at week 36.

11.5 Genetics Protocol Measures

Genetics protocol measures include one-time blood sample collection and completion of a Family Origin questionnaire. The blood sample should be collected at screening, but may be collected at any visit where there is a scheduled blood draw. The Family Origin questionnaire can be completed at any visit, ideally at the same time as the blood draw.

The Family Origin form is designed to be interviewer administered. It collects information about the participant and her/his biological family members' race/ethnicity, place of birth, and ancestry. If a participant does not know the information requested, the participant may answer "unknown".

12.0 STATISTICAL ANALYSIS

12.1 General Design

The primary goal of the study is to estimate the difference, if one exists, between XR-NTX and BUP-NX in the distribution of the time to relapse (i.e., loss of persistent abstinence) during the 6-month trial.

12.1.1 Primary and Secondary Outcomes (Endpoints)

Primary Endpoint: The primary outcome measure is the time to the event with the event called relapse. By definition individuals are abstinent at the time of randomization. Relapse occurs if the participant is using any non-protocol prescribed opioids regularly starting at day 21 post-randomization or thereafter. Operationally, loss of persistent abstinence is defined as either: (a) four consecutive opioid use weeks, or (b) seven consecutive days of use by self-report. A use week is defined as any week during which a participant self-reports at least one day of use during that week, provides a urine sample positive for non-protocol opioids, or fails to provide a urine sample. Self-report of opioid (heroin or prescription opioids) and other substance use is ascertained at each weekly study visit using the Timeline Follow-Back for each day leading back to the previous visit. Urine is collected at each study visit and tested for opioids. In the event that a participant reports no use, but their urine test indicates use, then the week is considered a use week. Missing urine samples are classified as positive. The time of the event occurs at the start of the qualifying clinical event period (e.g., first of the 7 consecutive use days or start of the 4 consecutive weeks of use).

Secondary Endpoints: Secondary endpoints include success of treatment initiation and selected opioid and other drug use measures as discussed in section 9.2. A set of additional secondary endpoints that describe adverse experiences and clinical states are detailed in that section.

12.1.2 Design

The therapeutic strategies defined above are evaluated and compared in a two-arm randomized open-label multi-center trial.

12.2 Rationale for Sample Size and Statistical Power

Original Projected Sample Size: 200 per treatment group. N = 400 total.

Data Analysis Modification Projected Sample Size: ~300 per treatment group. (N~600 total sufficient to enroll 350 late randomizers).

[figure not shown]
Rationale: The primary outcome is the time to relapse as defined above. Meta-analyses of randomized controlled trials of BUP-NX maintenance treatment for opioid dependence suggest that approximately 50% of patients are retained in BUP-NX treatment with good clinical outcome over 6 months.² Extended release naltrexone preparations have had few prior randomized comparisons but observations from a recent Russia-based trial evaluating the XR-NTX dose and formulation proposed for this trial had good results with 53% receiving all monthly injections and retained for 6 months. Direct randomized comparison of these approaches has not been performed.

We evaluate the anticipated variability of the primary terminal results by simulating under exponential distributional assumptions with event grouping over the first 21 days and using proportional hazards without censoring. Let one treatment have a 6-month success rate of 40% with exponential failure. We use a lower success target than indicated in the above paragraph because the use of the early randomization time point is expected to increase the percentage of

participants who are failures. There would be minimal impact on detectable alternatives if a higher 50% success rate was used. From the plot below, we observe that the 95% CI width for the hazard ratio for the 50th percentile of the simulation results under both the null and alternative hypotheses decreases by 31%, 19%, and 14% as the sample size increase by 50/arm from a base of 50/arm. CI width decreases by 11% when the sample size increases from 200/arm to 250/arm. We have selected 200/arm as subsequent precision improvements with this criteria are close to 10% per 100 sampling units.

Beyond a sample size of 150 to 200 patients per group, further increments in sample size (200 per group, 250 per group, 300 per group, etc.) yield diminishing returns in terms of only relatively small further narrowing of the 95% confidence interval. The rationale for increasing the total sample size to N ~600, in the event of a significant difference in induction success rate among early randomizers, is that given the current ratio of early to late randomizers, N ~600 total will yield approximately 250 early randomizers and 350 later randomizers. 350 late randomizers (N = 175 per treatment group) is close to the 400 (N = 200 per group) originally planned, and will yield a very similar (only slightly wider) 95% confidence interval. This will preserve the intent to achieve a relatively precise estimate of the difference in relapse rates among late randomizers.

Simulation results for the 50th and Upper 95th percentile of the 95% Confidence Interval Widths for the Hazard Ratio, selected sample sizes with lambda=0 and lambda=0.678

The decision theoretic properties of n=200/arm is evaluated further under a decision theoretic approach and using the logrank test. With two-sided alpha = 0.05, N = 400 total participants

provides 90% power to detect a hazard ratio of .63 for the second treatment. Table 4 provides additional characterization of power characteristics of the sample size.

Table 4. Detectable Alternatives and Power for 2-tailed 5% level logrank test without censoring Null distribution has a 40% 6 month success rate, N1=N2=200

Power (%)	Hazard Ratio	6 Month Survival Rate (%) under the Alternative
90.0	.633	56.0
80.0	.678	53.8

Note that inclusion of the baseline level of opioid dependence severity stratification variable in the statistical model as a covariate may increase power and narrow the confidence limits on treatment hazard ratios, should divergent success rates be present in the strata groupings.

Secondary analyses of moderators of treatment effect are important to trial sample size selection. With 200 XR-NTX cases evenly split between 2 levels of a classifying variable, we would have 79% power to detect, using a 2-tailed 5% level test of a binary endpoint, a 20 percentage point difference between the groups. Thus the selected sample size would be relatively robust in its ability to determine whether there are important differences in therapeutic success rates for major demographic or baseline clinical factors.

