5.2 Secondary Objectives

Secondary objectives are to:

1. Compare outcome on XR-NTX versus BUP-NX for the following domains:
 - a. Proportion successfully inducted onto assigned medication.
 - b. Safety, as measured by adverse events and serious adverse events, including opioid overdose episodes, both during the 6-month trial and during the 3-month follow-up period.
 - c. Opioid abstinence, as measured by the Timeline Follow-Back (TLFB) (self-report days using opioids), proportion of opioid-positive urine tests.
 - d. Misuse of alcohol and other drugs of abuse (e.g., cocaine, other stimulants, cannabis, benzodiazepines), by self-report and urine drug screens.
 - e. Tobacco use, as measured by the Fagerström Test for Nicotine Dependence (FTND).
 - f. Craving for opioids, and for other drugs, measured by Visual Analog Scales (VAS).
 - g. Depressive, anxiety, and subacute withdrawal symptoms (typical constellation is fatigue, anorexia, and insomnia), as measured by the Hamilton Depression Scale (17-item) (HAM-D) and the Subjective Opioid Withdrawal Scale (SOWS).
 - h. Problems related to drug abuse, as measured by the Addiction Severity-Index-Lite (ASI-Lite) and EuroQol (EQ-5D).
 - i. HIV risk behavior over time, as measured by the Risk Assessment Battery (RAB).
 - j. Cognitive function, as measured by performance on brief pen and paper tasks (Trail Making Test Parts A and B, Stroop).
2. Explore baseline demographic, clinical, and genetic features as predictors of opioid use outcome over the 6-month trial (main effect of predictors), and as moderators of differential treatment effect (moderator by treatment interaction).
3. Collect a limited dataset to permit analyses of economic costs and benefits of the two treatments.

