1.5 Randomization

Immediately following the final assessment of eligibility, participants will be randomly assigned to one of the two conditions: XR-NTX or BUP-NX. Random assignment will be on a 1:1 ratio to one of the two conditions. A restricted randomization plan will be used with centralized, automated, randomized block assignments. Randomization will be stratified by two factors, site and pre-detoxification level of opioid use. While there will be important and otherwise uncharacterized differences between sites – including state and local treatment service environments, opioid misuse epidemiology, and patient-level customs regarding treatment, medications, and clinical trial participation – the level of heroin and other opioid use will likely be an important independent predictor of treatment retention and rates of negative urines as has been demonstrated in recent analysis of naltrexone opioid trials (Sullivan et al 2006; Carpenter et al 2009; Brooks et al 2010). The level of opioid use at treatment entry is a binary classification, operationally defined as 6 or more bags (or equivalent) IV heroin per day (≥ 6 bags/day) over the 7 days prior to entry into the treatment program versus less than 6 bags (or equivalent) IV heroin per day (< 6 bags/day) or other routes of administration or other opioids.

Eligible participants will be randomized in a 1:1 ratio to the BUP-NX and XR-NTX arms. The randomization process will be performed by computer at a centralized location. Randomization will be stratified by site and pre-detoxification level of opioid use [≥ 6 or more bags (or equivalent) IV heroin per day (≥ 6 bags/day) over the 7 days prior to entry into the treatment program versus less than 6 bags (or equivalent) IV heroin per day (< 6 bags/day) or other routes of administration or other opioids]. The block size chosen will be adequate to ensure approximate treatment balance. The number in each treatment group will never differ by more than a factor of $KB/2$ where B is the block size and K is the number of strata.

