Beyond a sample size of 150 to 200 patients per group, further increments in sample size (200 per group, 250 per group, 300 per group, etc.) yield diminishing returns in terms of only relatively small further narrowing of the 95% confidence interval. The rationale for increasing the total sample size to N ~600, in the event of a significant difference in induction success rate among early randomizers, is that given the current ratio of early to late randomizers, N ~600 total will yield approximately 250 early randomizers and 350 later randomizers. 350 late randomizers (N = 175 per treatment group) is close to the 400 (N = 200 per group) originally planned, and will yield a very similar (only slightly wider) 95% confidence interval. This will preserve the intent to achieve a relatively precise estimate of the difference in relapse rates among late randomizers.

Figure 1: Simulation results for the 50th and Upper 95th percentile of the 95% Confidence Interval Widths for the Hazard Ratio, selected sample sizes with lambda=0 and lambda=0.678

The decision theoretic properties of n=200/arm is evaluated further under a decision theoretic approach and using the logrank test. With two-sided alpha = 0.05, N = 400 total participants provides 90% power to detect a hazard ratio of .63 for the second treatment. Table 2 provides additional characterization of power characteristics of the sample size.

Table 2: Detectable Alternatives and Power for 2-tailed 5% level logrank test without censoring Null distribution has a 40% 6 month success rate, N1=N2=200		
Power (%)	Hazard Ratio	6 Month Survival Rate (%) under the Alternative
90.0	.633	56.0
80.0	.678	53.8

Note that inclusion of the baseline level of opioid dependence severity stratification variable in the statistical model as a covariate may increase power and narrow the confidence limits on treatment hazard ratios, should divergent success rates be present in the strata groupings.

Secondary analyses of moderators of treatment effect are important to trial sample size selection. With approximately 200 XR-NTX cases evenly split between two levels of a classifying variable, we would have 79% power to detect, using a two-tailed 5% level test of a binary endpoint, a 20 percentage point difference between the groups. Thus the selected sample size would be relatively robust in its ability to determine whether there are important differences in therapeutic success rates for major demographic or baseline clinical factors.

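### The 79% power stated under moderators of treatment effect is for a subgroup contrast inside the XR-NTX arm; a 20-point moderator-by-treatment interaction has roughly 52–57% power at N=400

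*Protocol*

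**What the plan says.** The closing paragraph of Protocol 12.2 begins: "Secondary analyses of moderators of treatment effect are important to trial sample size selection". The one figure that follows is this: "With 200 XR-NTX cases evenly split between 2 levels of a classifying variable, we would have 79% power to detect". The effect in question is a gap of 20 points in a binary outcome between the two subgroups, tested two-sided at 5%. The paragraph then concludes that the sample size is relatively robust for finding differences in success rates across major demographic or baseline clinical factors. SAP 3.3 carries the same text with one softening: "With approximately 200 XR-NTX cases evenly split between two levels of a classifying variable, we would have 79% power to detect".

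Protocol 5.2, objective 2, separates two questions. Baseline features are to be explored as predictors of outcome (main effects) and "as moderators of differential treatment effect (moderator by treatment interaction"). Protocol 12.6 plans covariate-by-treatment interaction tests for baseline and genetic variables, and SAP 5.6 plans such tests for minority and gender status. Protocol 12.4 also plans a screen of baseline variables for subgroups within the XR-NTX arm; SAP 5.4 widens that screen to both treatment groups.

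**The concern.** A contrast inside one arm shows whether a factor predicts success on XR-NTX. It uses no BUP-NX participants, so it cannot show whether the factor changes the difference between the treatments. Protocol 2.0 describes moderators as variables that may help clinicians choose a treatment for a given patient, and that is an interaction question. The paragraph names the interaction question and then gives power for the predictor question.

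What is at stake is how a null moderator result is read. Someone who takes 79% as the power of the moderator analyses would treat a null finding as fair evidence against a 20-point moderator, when the chance of detecting one may be little better than even.

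**Working it through.** **Inputs from the documents**
- Within-arm contrast: 200 XR-NTX cases split 100 and 100, binary endpoint, 20 points, two-sided 5% (Protocol 12.2, SAP 3.3).
- Sample sizes: "Original Projected Sample Size: 200 per treatment group. N = 400 total"; "Data Analysis Modification Projected Sample Size: ~300 per treatment group"; 350 late randomizers, 175 per arm (Protocol 12.2).
- Allocation: "Random assignment will be on a 1:1 ratio to one of the two conditions" (SAP 1.5).
- With an even moderator split, each arm-by-moderator cell holds 100 (N=400), 150 (N~600) or 175/2 = 87.5 (late randomizers).

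**Assumed inputs.** Protocol 12.2 gives a 40% planning success rate for one arm but no subgroup rates. Cell rates of about 0.3–0.6 are assumed and varied below.

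**Step 1: reproduce the 79%.** For 100 versus 100 at 0.40 and 0.60:
- Uncorrected normal approximation: (0.20 − 1.96 × √(2 × 0.25/100)) / √((0.24 + 0.24)/100) = (0.20 − 0.1386)/0.0693 = 0.886, power 81%. At 0.30 versus 0.50 it is 83%.
- Continuity-corrected: subtracting 1/100 from the numerator gives 0.742, power 77%. At 0.30 versus 0.50 it is 79%.
- Fisher's exact test by enumeration: 78.7% (0.40 versus 0.60) and 79.2% (0.30 versus 0.50).

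The stated figure is therefore right for the within-arm contrast.

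**Step 2: the same 20 points as an interaction.** The estimate is a difference of two differences over four cells, so its variance is about twice that of the within-arm contrast:

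SE = √(Σ p(1 − p)/n), summed over four cells of size n; power = Φ(0.20/SE − 1.96).

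With XR-NTX 0.40/0.60 and BUP-NX 0.50/0.50, Σ p(1 − p) = 0.24 + 0.24 + 0.25 + 0.25 = 0.98.
- N=400: SE = √(0.98/100) = 0.0990; 2.020 − 1.960 = 0.060; power 52%.
- N~600: SE = √(0.98/150) = 0.0808; 2.474 − 1.960 = 0.514; power 70%.
- 350 late randomizers: SE = √(0.98/87.5) = 0.1058; 1.890 − 1.960 = −0.070; power 47%.

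**Step 3: vary the assumed rates**

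| XR-NTX; BUP-NX | N=400 | N~600 | 350 late |
|---|---|---|---|
| Variance at its maximum (0.5 in every cell) | 52% | 69% | 46% |
| 0.40/0.60; 0.50/0.50 | 52% | 70% | 47% |
| 0.40/0.60; 0.40/0.40 | 53% | 71% | 48% |
| 0.30/0.50; 0.40/0.40 | 54% | 71% | 49% |
| 0.30/0.50; 0.30/0.30 | 57% | 74% | 51% |

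A Wald test on the logit scale, run for the second to fourth rows, gives 51–54% at N=400 and 68–71% at N~600.

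**Step 4: interaction detectable with 80% power at two-sided 5%.** (1.96 + 0.84) × √(0.98/n) is about 28 points at N=400 and 23 points at N~600.

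**Step 5: the 10% level.** Replacing 1.96 with 1.645 at the Step 2 rates gives 2.020 − 1.645 = 0.375 (65%) at N=400 and 2.474 − 1.645 = 0.829 (80%) at N~600.

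**Step 6: like for like.** The interaction figures are uncorrected, so the matching within-arm figures are 81–83% with 200 XR-NTX cases and 94–95% with 300. The gap does not come from the choice of test.

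**The case against.** The strongest reply is that nothing is miscomputed. The paragraph states its inputs openly, the computed contrast fits the XR-NTX subgroup screen in Protocol 12.4, and Protocol 12.6 allows factors to be examined within each arm. The robustness sentence speaks of differences in success rates, which is what was computed. All of this stands. A reader might infer that the 79% is an arithmetic error, or that the trial lacks the stated power for the whole of objective 2. The documents support neither: the figure reproduces, and predictors of outcome are half of that objective.

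A second reply is that Protocol 12.4 and SAP 5.4 already say the study is not powered for an interaction. That remark concerns the severity stratum by treatment. It lowers expectations for other factors but does not qualify the paragraph in 12.2. Protocol 12.7 points the other way, saying that continuing to 350 late randomizers will make it possible to identify subgroups that benefit differently.

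A third reply is that the replacement figures depend on the chosen alternative. They do. If the factor works in opposite directions in the two arms (0.40/0.60 and 0.55/0.45), the interaction is 30 points, SE = √(0.975/100) = 0.0987, and power at N=400 is Φ(3.04 − 1.96), about 86%. The level matters too: the timing and severity interactions use p < 0.10 (Protocol 12.4, SAP 5.3.3 and 5.4). The two-sided 5% of SAP 3.5 applies where no other level is named, as for the minority and gender interactions in SAP 5.6. For these reasons the figures belong in the text as a range with stated assumptions.

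Finally, these analyses are exploratory, and SAP 3.5 promises cautious interpretation and confidence intervals. That limits the harm. That a null result would in fact be over-read is a risk, not something the documents show.

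**Conclusion.** The point holds as one of labelling and omission. The 79% is correct for a 20-point success-rate difference between two subgroups of 100 within XR-NTX, but it is offered under moderators of treatment effect, which the protocol itself defines as interactions. For an interaction of the same 20 points at two-sided 5%, power is about 52–57% at N=400, 69–74% at N~600 and 46–51% in 350 late randomizers. At the 10% level it is about 65% and 80% for N=400 and N~600.

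These figures assume cell success rates of about 0.3–0.6, an even moderator split (an uneven one lowers power) and an uncorrected Wald test. They use the binary endpoint of the plan's own paragraph, so they are not the power of the Cox-model interaction tests on time to relapse. The primary objective, sample size and planned models are unaffected.

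**What to change.** In Protocol 12.2 and SAP 3.3:
- Describe the 79% as power for a subgroup (predictor) contrast within the XR-NTX arm at 200 cases.
- Add the power for a 20-point moderator-by-treatment interaction at N=400, at N~600 and in the 350 late randomizers, with the assumed cell rates, split, significance level and range. Alternatively, state the interaction detectable with 80% power at two-sided 5%: about 28 points at N=400 and 23 points at N~600.
- Limit the sentence on robustness to differences in success rates within an arm.

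The cost is a few sentences and a less favourable stated figure. No design or analysis change is needed.
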